## 7.0 Setting

All participants will complete the study tasks in a dedicated research suite, the Psychophysiology Center, in the Brain Sciences Department within the IOP. The space to be used here is currently assigned to researchers on this study team and is well equipped for stimulus-controlled physiological recording. In addition, this space is used only for research protocols and thus is accessed at limited times. Studies assigned to this space may only enter during their assigned hours to ensure participant confidentiality and privacy. This also ensures COVID-19 related precautions may be taken: limiting use of space to no more than the participant and the study researcher and allowing time between participants for cleaning/sanitation, requiring the use of masks for researchers and participants.

## 8.0 Recruitment Methods

Participants will be recruited from the Charleston community and from the population of individuals who present to IOP for mental health treatment. Potential participants will be recruited via flyers (see advertisements) placed at approved sites at MUSC's library and hospital, as well as within the IOP; in addition, online advertisements will be placed on scra.org, on facebook.com, on researchmatch.org, and on nextdoor.com. Separate recruitment materials will either be targeted to adults seeking treatment for anxiety, mood, trauma-related or obsessive-compulsive disorder, or to the Charleston community at large. Appropriate approvals will be received prior to posting flyers.

When a potential participant contacts about the study, trained research assistants will overview all procedures and specify the expected duration and compensation (see Phone Recruitment script). The PI and Co-I will train staff in answering questions related to study procedures. After providing information about the study, a phone screener will be completed. Participants will be asked to complete this portion in a private setting. Should participants meet for the inclusion/exclusion criteria, and they agree participate, subjects will be provided with available participation dates, an online consent form, and will be sent the study's Redcap survey. They will also be provided with instructions on how to locate IOP and the lab space. Participants will be asked to refrain from alcohol use and intense physical activity 24 hours before the study, as well as refrain from caffeine 6 hours and tobacco 2 hours prior to the study. Participants will be encouraged to sleep as they usually do the night before the study.

In order to recruit participants with implanted VNS, the principal investigator will contact clinicians at MUSC to disseminate information about this study to patients with VNS, including the MUSC Center for Rehabilitation Research and the MUSC Comprehensive Stroke Center. Clinicians and researchers will be provided a script (see VNS Recruitment Script). Clinicians will be asked to only invite patients: 1) who have completed VNS treatment/research or 2) whose VNS treatment/research protocol will not be affected by 30 minutes of stimulation.

## 9.0 Consent Process

The consent form will be sent to participants via RedCap after the phone screen is complete and prior to being sent the RedCap surveys. Participants will be given ample time to read the consent form and a researcher will describe the content of the consent form to ensure understanding, including describing the laboratory measures, study duration, and equipment and materials. The researcher will describe confidentiality/privacy measures, participant right to withdraw, risks/benefits, and compensation. In addition, participants will be prompted to ask questions throughout consenting to further ensure understanding. After electronically signing the consent form, an electronic copy will be made accessible to the participant for their records. They will also be offered a hard copy which will be provided during the in-lab scheduled participation date.

## 10.0 Study Design / Methods

After completing the phone screener, participants will be invited to in-lab participation: they will be provided available times and instructed on how to locate IOP and the laboratory space. They will be asked to refrain from the following prior to the study: Tobacco use within 2 hours, Caffeine within 6 hours, Alcohol within 24 hours, and intense physical activity within 24 hours. Participants will be asked to sleep as they usually do the night before the study. The study will take up to two hours and thirty minutes.

Prior to arrival to the research space, after phone screening, participants will be provided online informed consent (see Section 9.0). After participants have been informed of the nature of the study and consent to the study procedures, they will be sent a series of questionnaires to be completed online using the RedCap survey platform. They will be asked to complete these questionnaires in a private setting to ensure their confidentiality. None of the items on these questionnaires address suicidality. However, surveys will be monitored for extreme scores indicating severe mental health issues or indication of suicidal or homicidal ideation/risk, and those participants will be contacted *immediately* via phone to assess for safety. Several attempts will be made to reach at risk participants. They will be assessed for safety again, upon arrival to the lab. Questionnaires will include a measure of demographics, Penn State Worry Questionnaire (PSWQ; Meyer et al., 1990), the Attentional Control Scale (ACS; Derryberry & Reed, 2002), the Childhood Trauma Questionnaire (CTQ; Bernstein & Fink, 1998), Connor Davidson Resiliency Questionnaire (Connor & Davidson, 2003), Contrast Avoidance Questionnaire (CAQ; Llera & Newman 2017), PTSD Symptom Scale – Self-Report (PSS-SR; Falsetti et al., 1993), the Perseverative Thinking Questionnaire (Ehring et al., 2011), the Social Interaction Anxiety Inventory/Social Phobia Scales Short forms (SIAS-SPS; Fergus et al., 2012), the Intolerance of Uncertainty Scale (Carleton et al., 2007), Difficulties with Emotion Regulation Scale (Gratz & Roemer, 2004), and the Generalized Anxiety Disorder 7-item scale (GAD-7; Spitzer, 2006).

Once participants have arrived to the laboratory, if they identify as an individual of childbearing potential, they will be provided with a pregnancy test strip to take in privacy. They will be provided instructions on how to use the test, as well. After completing the pregnancy test, participants with negative results will be asked to continue to the remaining study procedures, whereas those with a positive result will be debriefed, compensated for their time, and released.

Next, electrodes will be attached which will measure a variety of responses, including electroencephalography, electrocardiography, electrooculography, electromyography (startle reflex), and electrodermal activity. Tobii eye tracker software will be set-up to monitor and record pupil dilation and eye tracking. TaVNS electrodes (active and sham) will be attached to participants who do not have implanted VNS. A computer monitor will be adjusted for appropriate eye level. Peripheral physiology (e.g., heart rate) data will be collected using a Biopac MP150 hardware and amplifier along with AcqKnowledge software, and brain activity will be collected using an Actichamp active sensor cluster and amplifier. Stimuli (e.g., learning tests) will be presented using Presentation software. The following questionnaires will be administered during electrode set up: Positive and Negative Affect Schedule – Short Version (PANAS; Thompson, 2007), the Beck Depression Inventory- II, (BDI-II; Beck et al., 1996), State Trait Anxiety Inventory (STAI; Spielberger et al., 1983), the Anxiety sensitivity index (ASI-3; Taylor et al., 2007). Participants will be asked when they last used Tobacco, Caffeine, Alcohol, engaged in intense physical activity, and when they last took medication, along with what those medications include. They also will be asked to report on their typical sleep habits and sleep from the night before – these will be asked in the Health Behaviors Survey. A measure of tolerability for

stimulation will be administered periodically throughout the study. Responses (particularly those on the BDI-II (Item #9 – suicide ideation) will be monitored for endorsements of suicidal ideation. See section 13 for study team response to suicidal ideation.

After all electrodes are attached, a 1) baseline (5-10 min) physiology measurement will be taken. Then stimulation will begin. See additional information in Section 3.0 (Intervention to be Studied). Participants in the taVNS group (not having implanted VNS) will be randomized to one of 9 doses with 5 participants per dose, increasing in 10 minute increments of active stimulation. All active sessions per dose will be delivered contiguously and at the end of the stimulation period, and sham stimulation at the beginning. This is to ensure that all participants have the same lapse of time between pre- and post-stimulation recording. That is, if a participant is randomized to 60 minutes of active stimulation, the first 30 minutes would be sham stimulation.

For participants with previously implanted vagus nerve stimulation devices, stimulation will be delivered for 30 minutes. They will subsequently be invited to revisit the lab to receive non-invasive taVNS delivered in a comparable manner to the healthy subjects for 30 minutes.

Additional physiology measurements will be taken 2) concurrent with stimulation and during a final recovery measurement (5-10 mins) after stimulation has concluded.

During the base, recovery, and during 3 time points during the 90-minute stimulation period (i.e., 30 minutes, 60 minutes, and 90 minutes), a Passive Auditory Oddball Task will be administered. During this task a relaxing movie (i.e., silent sand art film) is presented concurrent with standard and deviant tones; MMN task from the ERP Compendium of Open Resources and Experiments - ERP CORE; Kappenman et al., 2020; Eriksen & Eriksen 1974).

For participants with previously implanted VNS devices, the same Passive Auditory Oddball task will be administered. Additional tasks will be administered, including a visual search task, during which an array of shapes are presented on a computer screen. Participants must identify and click on a target shape (N2pc task from the ERP Compendium of Open Resources and Experiments - ERP CORE; Kappenman et al., 2020). A cued picture viewing task will be administered consistent with other research at MUSC department of psychiatry studies. Cues (shapes) are presented followed by either an unpleasant, pleasant, or neutral picture. Pictures are from the International Affective Picture System (Lang et al., 2005). Similar research is being conducted at MUSC by co-investigator [name] using these pictures and task design. Finally, a fear learning and extinction task will be administered. Participants will see different shapes/colors appear on the computer screen. Some of the shapes/colors will be paired with the sound of a person screaming (Glen et al., 2012). White noise bursts will be played during these tasks at random times.

During the physiology/task assessment participants will be provided with a brief break from computer tasks. During this time, the Montreal Cognitive Assessment (MOCA; Nasreddine, 2004) will be administered to ensure there is no major cognitive decline.

Then a 3) finally during a recovery period (5-10 min) resting physiology measurement will be taken. After all the tasks are completed, participants will be debriefed about the purpose of the study, compensated for their time, and released. Participants will be reimbursed using a ClinCard with the amount of \$100. They will be provided with the ClinCard along with relevant information (e.g., ATM withdrawal fees, how to use) prior to leaving the in-lab procedures.

Participants with implanted VNS will be asked to return for a second visit, during which they will receive no stimulation, but will be asked to complete the same tasks. The order of stimulation versus no

stimulation lab visits will be randomized. They will be reimbursed using a ClinCard with the amount of \$180 for the first 2 lab visits and surveys. Should participants with implanted devices agree to a third in-lab visit for 2.5 hours, they will be reimbursed with an additional \$80.00 to their ClinCard.

Several procedures will be taken to minimize risks over the course of the study:

**Physiology:** For sensors that are attached to skin there is some risk for mild local irritation or redness, thus adhesives are removed with caution/gently. Participants are informed that EEG involves the use of a water based gel during the consent process as some participants report they dislike having the gel in their hair. There are rare instances of static shock during EEG. Thus participants are seated in non-metal chairs and experimenters use caution so as to not increase risk of electrical shock, such as using a grounded EEG system.

**TaVNS:** The taVNS stimulation administered during the *study is non-invasive but includes some risk*. Participants will be screened for potential contraindications to taVNS prior to invitation to the lab (see Section 5.0 for exclusion criteria; e.g., ear trauma/pain, metal implants). The device has safety mechanisms to prevent electrical surges. Skin will be prepared using 70% alcohol swabs prior to electrode attachment to ensure sanitation and stimulation power is safe. Metal jewelry also will be removed from the head. Stimulation is applied using similar electrodes to those used in EEG and a water based conductive gel, and participants will be assessed after application/prior to stimulation for discomfort related to the electrode. Participants will be assessed during stimulation for discomfort or adverse events over the course of stimulation, though studies have demonstrated few concerns of safety. Participants are encouraged to share report of discomfort and are reminded prior to the study they may discontinue at any point. The ear also will be cleaned and inspected for irritation/redness after stimulation. The ear stimulation delivered during the study includes some risk. Participants in previous research using this stimulation describe the feeling as a “tickle” or “pricking” sensation. Some report mild irritation. Our researchers will inspect the ear after stimulation given previous research has documented some redness from the stimulation.

**VNS:** Participants being recruited to complete this study with VNS, will include subjects with previously implanted devices and who have been given permission by their physician to activate their own stimulator without health risks. These participants who may administer their own stimulation have been given a “magnetic wand” or button to activate their stimulator in order to encourage post-stroke motor function. No severe adverse effects have been reported with implanted devices after implantation. However, mild discomforts/risks have been reported including nausea and dysphagia (swallowing difficulties) which resolve by the end of the day after stimulation. Participants will be encouraged to report discomfort and will be assessed periodically for these discomforts. To ensure that ongoing VNS treatment is not affected, only those who have completed VNS treatment/research or whose VNS treatment/research will not be affected by 30 minutes of stimulation will be recruited for the study.

**Surveys:** Some report mild discomfort when reporting on these topics, so study staff, including the PI and Co-I, will be available to debrief participants in distress, if needed. The PI will be available to provide counseling resources if participants are interested, and in the case of suicidal ideation and intent (see Section 13.0) immediate and appropriate response will be provided, including encouraging the participant to remain with experimenters (even if study is terminated) to ensure the participant is in a safe location. The study personnel are clinically trained to identify participants in distress. However, these surveys involve minimal and low-base rate for risk.

Tasks: The tasks involve no more than minimal risk. The scenes and tones played during the study are not distressing in nature. To ensure comfort, participants will be allowed to adjust to the tones starting the task. Participants will be monitored for distress. For participants with implanted VNS who complete the fear learning task, the screaming sounds can generate mild temporary distress. Studies show that this mild temporary distress typically dissipates by the end of the task, as it includes a phase of “fear extinction” where symbols are presented unpaired with a feared stimulus. The picture viewing task, used in several studies here and at other research labs, consists of some unpleasant pictures, which can evoke sadness or fear. However, these feelings do not persist beyond the picture viewing task and participants who report sadness or fear indicate the emotions are of a manageable intensity. Participants will be assessed for these discomforts throughout, and will be monitored for extreme discomfort. Should participants indicate the discomfort is of extreme intensity, the tasks will be discontinued. Participants may discontinue at any point without consequence.

Confidentiality: To protect confidentiality of study-specific measures, only the participant code, and no potentially identifying information (e.g., name, date of birth) will ever be associated with these measures. In addition, self-report data will not include identifiable information. Self-report data are in Likert format and will be linked only to a participant code. Thus, no data will be identifiable. However, there is still a small risk of loss of confidentiality of participant information in this study. Steps taken to protect confidentiality are described further in the **Data Management** section.

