Participants will be randomized to one of 9 dose durations with 5 participants per dose, increasing in 10 minute increments of active stimulation, ranging between 10 and 90 minutes of stimulation. All active sessions per dose will be delivered contiguously and at the end of the stimulation period, and sham stimulation at the beginning. This is to ensure that all participants have the same lapse of time between pre- and post-stimulation recording. That is, if a participant is randomized to 60 minutes of active stimulation, the first 30 minutes would be sham stimulation. After establishing the optimal dose-duration a sample of treatment seeking individuals will be recruited. This dose will be administered to individuals with anxiety and trauma symptoms to ensure that effects are sustained and to determine feasibility and tolerability.

An additional group of individuals with implanted VNS also will be evaluated after 30 minutes of stimulation. Patients at MUSC who participated in the Microtransponder Vivistim trial or other research/treatments involving VNS will be recruited to complete similar cognitive and affective tasks while psychophysiological responses are measured across 3 sessions: control (no stimulation), implanted VNS, and noninvasive taVNS. This will serve as a comparator for whether taVNS is activating similar brain and physiological regions as invasive forms of vagus nerve stimulation. This will also indicate whether mechanisms of taVNS and VNS are comparable. In order to truly determine comparability of these two forms of VNS, it is imperative to assess within subject brain, body, cognitive, and emotional responding across both implanted and non-invasive VNS.

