EEG will be measured using a 32-channel BrainVision actiCHamp system. Data will be processed with BrainVision Analyzer software. Resting EEG will be measured pre-, post-, and concurrently with stimulation, and will be explored for taVNS dose dependent modulation in frequency bands and coherence of the **EEG power spectrum**. For data collected during the learning/attention task, multiple **event-related potentials** (ERPs) and **steady-state visually evoked potentials** (ssVEPs) will be assessed. A variety of ERPs indicative of attention (i.e., orienting, discrimination) will be evaluated across a variety of contexts after stimulation, including fear learning and extinction, and learning more broadly. Some studies have shown taVNS linked enhancements in the P300, an orienting response (Warren et al., 2020), whereas other studies have not (Warran et al., 2019; Keute et al., 2019). A recent evaluation found taVNS related ERP modulations indicative of enhanced cognitive control (i.e., N2; Pihlaja et al., 2020), which is typically increased during engagement of attention and is enhanced during cognitive conflict. Enhancements in the N2 are typically seen across internalizing disorders, and our previous work demonstrates that the N2 is modulated under internal and external threat (Taylor et al., 2020; Moran, Taylor, & Moser, 2012; White, Grant, Taylor et al., 2018). In addition, ssVEPs which are collected by flickering visual stimuli, may be assessed during stimulation. These potentials are modulated by attentional and motivational factors and will provide real-time dose-dependent data regarding taVNS related modulations in attention. Given the extant and emerging literature on the effects of taVNS on brain activity, these ERPs and other relevant ERPs will be explored.

Participants will complete subjective measures of anxiety and depression and related difficulties as well as Self-Reported Units of Distress (SUDs) during stimulation and the tasks and acceptability/tolerability measures (see Section 10.0 Study Design/Methods for surveys and other measures).

The above measures will also be assessed for participants with implanted invasive VNS and then subsequently with noninvasive taVNS.

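### In the implanted-VNS cohort the order of VNS and taVNS is not balanced: taVNS always follows VNS and is most likely always the third visit, so Exploratory Aim 3 is confounded with visit order.

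*Combined protocol and SAP*

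**What the plan says.** Section 3.0 states that in implanted patients "psychophysiological responses are measured across 3 sessions: control (no stimulation), implanted VNS, and noninvasive taVNS", and presents this within-person contrast as the way to judge whether the two forms of stimulation are comparable. Exploratory Aim 3 in Section 1.0 rests on it.

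The visit order has to be pieced together:

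- Section 10.0, after describing the implanted-VNS stimulation: "They will subsequently be invited to revisit the lab to receive non-invasive taVNS".
- Section 4.0 gives the same sequence: "implanted invasive VNS and then subsequently with noninvasive taVNS".
- Section 10.0 on the control visit: "Participants with implanted VNS will be asked to return for a second visit, during which they will receive no stimulation". The next sentence says that the order of stimulation versus no "stimulation lab visits will be randomized".
- Section 10.0 on payment: one sum is given "for the first 2 lab visits and surveys", and a further sum follows for an optional third visit: "Should participants with implanted devices agree to a third in-lab visit for 2.5 hours".

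The tasks for this cohort are the passive oddball, visual search, cued picture viewing, and fear learning with extinction. Section 10.0 says the tasks at the no-stimulation visit are the same. Section 3.0 describes the tasks across the three sessions only as similar. For this comparison the plan gives no three-way balancing of order, interval between visits, visit term or analysis method. Section 1.0 expects fewer than five such patients; Section 6.0 gives five.

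**The concern.** A within-person comparison removes differences between patients but leaves differences between visits. Patients may respond less, or differently, when they meet the same or similar tasks again, and fear learning with extinction is itself a learning procedure. The protocol guards against this for VNS versus no stimulation by randomising their order. It gives no such protection to VNS versus taVNS, the contrast that Exploratory Aim 3 needs.

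The resulting error is systematic. It could create a difference between the two forms of stimulation or hide one, and recruiting more patients would not reduce it. A finding that VNS and taVNS act alike would be as hard to interpret as a finding that they differ.

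The text is also unclear on a related point: Section 10.0 calls the no-stimulation visit the second visit and then randomises its place.

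**Working it through.** The plan states no sample size, test or error rate for this comparison, so there is no figure to reproduce. The check enumerates the visit orders and asks what can be estimated. V is implanted VNS, C is no stimulation and T is taVNS.

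**1. Orders allowed on the natural reading.** V and C are randomised within the first two visits and T is third. The sequences are V-C-T and C-V-T.

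- Expected position of V: (1 + 2)/2 = 1.5
- Expected position of C: (2 + 1)/2 = 1.5
- Position of T: 3.0
- Gap, T minus V: 3.0 − 1.5 = 1.5 visits

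**2. Can a visit term separate them?** Take a linear model with patient, visit (three levels) and condition (three levels).

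| Design | Columns | Rank | T − V estimable? |
|---|---|---|---|
| Natural reading, 5 patients | 5 + 2 + 2 = 9 | 8 | No |
| Natural reading, 4 patients | 4 + 2 + 2 = 8 | 7 | No |
| 5 patients on 5 different orders of the six | 9 | 9 | Yes, variance 0.42σ² |
| 6 patients on all six orders | 10 | 10 | Yes, variance 0.33σ² |

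In the first two rows the taVNS column is identical to the visit-3 column. V − C remains estimable. The randomised pair informs the change from visit 1 to visit 2, but nothing identifies the change from visit 2 to visit 3.

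**3. Alternative reading.** Suppose the no-stimulation visit may fall last, so that V-T-C is also possible. A mix of V-T-C and C-V-T, for example, has rank 9 of 9 with five patients, and T − V becomes estimable if a visit term is fitted. The plan fits none. T still comes one or two visits after V in every sequence, so an analysis without visit remains biased by at least one visit's drift.

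**4. Size if visit is ignored (assumptions, not in the documents).** Let the visit effects be 0, e/2 and e, in SD of the within-person difference, with no true difference between V and T. On the natural reading:

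bias = e − (0 + e/2)/2 = 0.75e

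- e = 0.5: 0.75 × 0.5 = 0.375, about 0.38 SD
- e = 1.0: 0.75 × 1.0 = 0.75 SD

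Simulating 200,000 datasets per case with a two-sided 5% one-sample t-test on T − V gives these false-positive rates:

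| Patients | e = 0.5 | e = 1.0 | All three orders randomised |
|---|---|---|---|
| 5 | 10% | 24% | about 5% |
| 4 | 8% | 18% | about 5% |

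**5. Does simple randomisation of all three visits suffice?** Only on average. With five patients drawn independently from the six orders and e = 1.0, the mean absolute imbalance in a realised sample is 0.25 SD, and 28% of draws reach 0.375 SD or more. With five different orders, the gap is 1/5 = 0.2 or 2/5 = 0.4 visits at 0.5 SD per visit, that is 0.1 or 0.2 SD. A visit term then accounts for the remainder.

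**The case against.** The strongest reply is that the order is inferred. A reader might conclude that the protocol fixes taVNS as the last visit and that no analysis could ever separate it from repetition. The documents do not go that far. No sentence names the third visit as taVNS, both VNS and taVNS visits are stimulation visits, and under the alternative reading in step 3 a visit term would work. The paired payment makes the natural reading the more likely one. What survives either way is that both sections that order the two conditions put VNS first.

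A reader might also infer that by the third visit patients have seen the same pictures twice and extinguished the same fear cue twice. The documents do not say that pictures or cues are reused, and Section 3.0 says only that tasks are similar. Repetition effects are plausible, but their size is unknown.

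Outcomes are not equally exposed. Section 10.0 takes a baseline recording before stimulation and gives the oddball at baseline and recovery. Change from the same visit's baseline would remove a simple shift in level for resting and oddball measures. It would not remove a change in reactivity, and it does not help fear learning, picture viewing or visual search.

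Finally, Section 12.0 specifies MCP-Mod for dose-response only. The false-positive rates above therefore belong to a test that the plan does not contain. That limits them to illustration; the aliasing in step 2 does not depend on them.

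**Conclusion.** The concern holds in limited form. On the most natural reading, taVNS is the optional third visit and its contrast with VNS cannot be separated from visit order. On any reading, taVNS follows VNS and the two are unbalanced for order. The aliasing depends only on that reading of the sequence. The bias of 0.38 to 0.75 SD, and the error rates that go with it, rest on an assumed linear drift of 0.5 to 1.0 SD, an analysis without a visit term, and a t-test not in the plan. The concern is greatest for fear learning, picture viewing and visual search, if the same or similar tasks are repeated.

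The scope is narrow: Exploratory Aim 3, with at most five patients. It would be wrong to infer that the dose-response work in Aims 1 and 2, or the tolerability aim, is affected, because none of them uses this comparison. The change is still worth making, since it is cheap and Section 3.0 draws a conclusion about comparable mechanisms from these data.

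**What to change.** In Section 10.0:

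1. State in one place which condition is given at which visit, and reconcile the description of the no-stimulation visit as the second visit with the randomisation of its order.
2. For patients who agree at consent to three visits, assign the order of VNS, no stimulation and taVNS from a balanced list without repeated sequences, drawn from the six possible orders. Arrange the list so that it stays as balanced as possible if only four patients enrol.
3. Keep the present two-visit randomisation for patients who agree to two visits only.
4. Include visit number in the analysis or, with so few patients, report results by visit number.

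This needs a new order list and revised consent wording, but no added visit, patient or procedure. It has two costs. A patient who stops after an early taVNS visit may lack the VNS visit, which matters with so few patients. The small cohort may also be split between two-visit and three-visit lists.

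If the sponsor keeps the fixed order, the protocol should say that the VNS versus taVNS comparison is descriptive and confounded with visit order.
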